(5d) This study will obtain data generated from other sources. Examples may include receiving data from participating sites or an external collaborator, accessing an external database or registry, etc. Explain the source and how the data will be used in the Methods section.

(6) Video audio recording: *Describe the plan to maintain subject privacy and data confidentiality, transcription, store or destroy, etc.*

HIPAA Identifiers and Protected Health Information (PHI)

Protected health information is medical data that can be linked to the subject directly or through a combination of indirect identifiers.

Recording identifiers (including a code) during the conduct of the study allows you to return to the medical record or data source to delete duplicate subjects, check a missing or questionable entry, add new data points, etc. De-identified data is medical information that has been stripped of all HIPAA identifiers so that it cannot be linked back to the subject. De-identified data is **rarely** used in the conduct of a research study involving a chart review.

Review the list of subject identifiers below and, if applicable, check the box next to each HIPAA identifier being recorded at the time of data collection or abstraction. Identifiers apply to any subject enrolled in the study including Mayo Clinic staff, patients and their relatives and household members.

Internal refers to the subject's identifier that will be recorded at Mayo Clinic by the study staff.

External refers to the subject's identifier that will be shared outside of Mayo Clinic.

Check all that apply:	INTERNAL	EXTERNAL
Name		
Mayo Clinic medical record or patient registration number, lab accession, specimen or radiologic image number		
Subject ID, subject code or any other person-specific unique identifying number, characteristic or code that can link the subject to their medical data	X	X
Dates: All elements of dates [month, day, and year] directly related to an individual, their birth date, date of death, date of diagnosis, etc.		
Note: Recording a year only is not a unique identifier.		
Social Security number		
Medical device identifiers and serial numbers	X	
Biometric identifiers, including finger and voice prints, full face photographic images and any comparable images		
Web Universal Resource Locators (URLs), Internet Protocol (IP) address numbers, email address		
Street address, city, county, precinct, zip code, and their equivalent geocodes		
Phone or fax numbers		
Account, member, certificate or professional license numbers, health beneficiary numbers		

Vehicle identifiers and serial numbers, including license plate numbers		
Check 'None' when none of the identifiers listed above will be recorded, maintained, or shared during the conduct of this study. (exempt category 4)	 None	 None

Data Analysis

Power analyses may not be appropriate if this is a feasibility or pilot study, but end-point analysis plans are always appropriate even if only exploratory. Provide all information requested below, or provide justification if not including all of the information.

Power Statement:

Population Justification:

We have determined that healthy volunteers should be sufficient to validate the metrics of tidal volume and respiratory rate, due largely to the fact that healthy volunteers are able to breathe through a range of respiration rates and tidal volumes without putting their health at risk. Using the intended use population, who are generally ailing, struggling to breathe normally, and elderly, we would likely not be able to cover the full range of measured values with as much standardization as we would like to in this protocol. The mode of operation of the device and its use does not change whether a subject is healthy or part of our intended use population, and thus we believe that whether this data comes from healthy or ill volunteers does not matter in this case.

Sample Size Justification:

Based on prior studies data, the mean error (e.g., bias) of the respiration rate across 6 and 40 bpm ranges between -0.02 and -0.16 bpm, and the standard deviation of the error ranges between 1.74 and 3.31 bpm. To demonstrate the mean error is less than ± 1 bpm, we will use a worst-case scenario of the mean error of -0.16 bpm with a standard deviation of 3.31 bpm. For two-sided hypothesis testing with significance level ($\alpha=0.05$) and with 90% power ($\beta=10\%$), the minimum sample needed across 6-40 bpm is 202. Given that 9 readings will be collected per each participant, the minimum number of subjects is 23.

In addition, based on the prior study, the root mean squared residual relative errors after linear fitting ranges between 25.2 and 30.4%. To demonstrate that the root mean squared residual errors after liner fitting is less than 35% based on the hypothesis testing Chi-squared test with significance level ($\alpha=0.05$) and 95% power ($\beta=5\%$), the minimum sample needed is 136. Given that 8 readings will be collected per each participant, the minimum number of subjects is 17.

However, to better reflect a broader patient population and since we might be under-estimating our error, we plan to enroll 40 subjects (up to 60 subjects, if necessary).

Data Analysis Plan:

Demographics:

A table will be constructed with counts and percentages of the number of subjects who were screen failures, the number of subjects enrolled in the study, the number of subjects withdrawn from the study before study completion, and the number who completed the study. For those subjects who withdrew before completion of the study, counts and percentages of the reasons for withdrawal will be tabulated. The continuous demographic characteristics at screening will be summarized for all subjects enrolled in the study using descriptive statistics (mean, standard deviation, median, minimum, maximum, and number of non-missing observations). The categorical baseline characteristics will be summarized for the study participants using frequency counts and percentages.

Effectiveness and Endpoint Analyses:

Respiration rate and relative tidal volume from the CPM System will be derived from the CPM analytics engine as described previously in the protocol, and the equivalent parameters and study data will be recorded from the reference device output. The reference respiration rate will be derived by trained medical professional annotating the number of breathing cycles in the recorded capnography waveform in the time period corresponding to the CPM readings.

For pairs of respiration rate calculated by the CPM and the reference, Bland-Altman analysis will be conducted to evaluate the accuracy of the respiration rate.

For pairs of relative tidal volume (rTV) calculated by the CPM system and tidal volume measured by the reference device, the correlation coefficient and R^2 value for the tidal calculated. In addition, the root mean squared of the residual errors after linear fitting will be calculated to characterize the relative errors of the relative tidal volume.

Endpoints:

Respiration Rate Accuracy

- 85% respiration rate error $\leq \pm 2$ BPM between reference and test device at 6-40 BPM

Relative Tidal Volume Relative Accuracy

- Root Mean Squared (RMS) of residual error after linear fitting $\leq 35\%$

Respiration Rate Endpoint Justification

The Respiration Rate is derived by the CP Analytics Engine from impedance measurements taken by the CPM device for a one (1) minute period. The CP Analytics Engine performs a quality control (QC) check for at least 30 seconds of consecutive impedance measurement samples. This QC-validated measurement data of at least 30 seconds results in a maximum computational accuracy of 2 BPM for the respiration rate. Consequently, an accuracy of 2 BPM is deemed sufficient for the CPM Device's intended use.

Relative Tidal Volume Endpoint Justification

Relative Tidal Volume as measured by an implanted device have shown to have day-to-day variability ranges between 10% and 14% in terms of coefficient of variation (Boehmer et al., *Journal of Cardiac Failure*, vol. 18, no. 8S, Aug, 2012). In addition, breath-to-breath tidal volume variability ranges from 18% to 43% depending on the underlying pulmonary disease conditions (Kuratomi et al. *Japanese Journal of Medicine*, vol. 24, no. 2, May, 1985), which further supports that day-to-day variability can be as high as 14%. Given this physiological day-to-day variability, it is considered that as high as 35% (about 2.58 times, $Z_{99.5\%}$, of 14%) of change can be

considered physiologic unless other clinical information strongly indicates otherwise. To correctly indicate the change greater than 35%, the relative error less than 35% is deemed sufficient to trend and indicate clinically significant change of rTV.

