- Respiration Rate and relative changes in Tidal Volume
- Heart Rate
- Diastolic Heart Sounds Strength
- Body Posture (including Tilt Angle)

The device is intended for use on general care adult patients who are 18 years of age or older to provide physiological information. The data from the ADI CPM System are intended for use by healthcare professional as an aid to diagnose and treatment.

The ADI CPM System is intended to be used by patients at rest and not performing any activities or movements. This system is for spot checking and does not have continuous monitoring capability. The device does not produce alarms and is not intended for active patient monitoring (real-time).

The computer-generated analysis of ECG data displayed by the CPM system is intended for informational use only. The ECG waveform and analysis are meant to supplement currently used methods of rhythm classification for the purposes of discriminating atrial fibrillation from sinus rhythm and not intended to replace traditional

[figure not shown]
methods of diagnosis or treatment. The interpretation of ECG offered by the device are only significant when used in conjunction with a physician overread as well as consideration of all relevant patient data.

The ADI At-Home CPM System is contraindicated for:

- Those patients with life threatening arrhythmias requiring immediate medical intervention.

CPM System Raw and Derived Measurements:

The CPM Analytics Engine derives measurements such as heart rate, respiration rate, relative tidal volume, thoracic impedance, body posture, diastolic heart sounds strength, and possible atrial fibrillation from raw measurement data acquired from the CPM device's sensors and electrodes. The raw measurements taken by the device and their derived parameters are illustrated in the graphic below. For this study, the focus will be on the impedance pneumography and the respective derived parameter measurements from each of these raw parameters.

Respiration Rate and Relative Tidal Volume Derivation:

Streaming of impedance is measured across the left side of the chest using 100kHz excitation frequency and streamed/sampled at a rate of 50 samples per second.

An algorithm is used to process the stream of impedance data and extract changes in impedance caused by breathing (i.e., relative tidal volume). Similarly, the rate of these changes in thoracic impedance is used to calculate the respiration rate.

Reference Devices:

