Participants who have verbally consented will be asked to complete the informed consent form and return it to the clinical staff before the start of the study. Participants will be provided a copy of the informed consent for their records. No patient data will be collected prior to this. Once the form has been signed, the study can begin.

Written consent will be obtained, documented, and maintained as part of the research records. No identifiable patient information will be maintained, other than a randomly assigned subject number and patient ID that is generated by the CPM System.

Pre-Screening:

Before signing the Informed Consent form, subject will be screened by the study team for eligibility based on the inclusion and exclusion criteria.

Baseline Evaluation:

The following evaluations are required at the time of subject enrollment:

1. Medical history and current status – skin disorders;
2. Medical history and current status – allergies;
3. Medical history and current status – electronic implants;
4. Medical history and current status – cardiopulmonary disorders or illnesses including date of onset, recent hospitalizations and/or treatments, and medications taken;
5. Evaluation of device application site for broken, damaged, or irritated skin or rashes;
6. Demographics information: Age, Gender, Height, Weight, Race, Ethnicity, Occupation

7. Other information: smoking history, alcohol use (self-reported), recreational drug use (self-reported), Caffeinate intake, exercise habits
8. Body temperature via tympanic thermometer.

These assessments will be recorded in the CRF. Subjects who meet all inclusion and none of the exclusion criteria for either of the cohorts will then be able to proceed with the study and will be considered enrolled once measurement capability of the device on the subject has been verified.

Risks and Benefits:

Participating in this study poses minimal risk to participants. The ADI CPM Device is a non-significant risk, noninvasive medical monitoring device. The device is IEC 60601 compliant and meets all standards needed for FDA approval. There is slight risk that the adhesive used on both the reference and test devices will cause mild skin irritation due to prolonged adhesion of the devices as well as hair in the area. If this is case, the participant can decide to stop the study at any time. Hair in this area may also have to be trimmed if initial data collection proves to be a challenge. This will be done by the study team.

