This research study will be conducted in [name] laboratory in the Joseph building at St. Mary's hospital. The laboratory is equipped with all necessary equipment to perform human physiology experiments in a safe and secure environment. The study team has a long history of conducting Mayo IRB approved research protocols involving controlled breathing exercises in healthy participants. All personnel involved with this study have completed human subject protection certification such as CITI training. The combined expertise of the study team and the Sponsor will ensure that this research project is conducted safely and completed in a timely manner. This study has no financial implications for Mayo Clinic other than person hours required to recruit patients and run the study. All materials related to the CPM System (under test) used in the study will be provided by Analog Devices, and the reference devices and materials (SpO2 monitor, spirometry device, metabolic cart, ECG devices) will be supplied by [name] lab.

(1a) This is a multisite study involving Mayo Clinic and non Mayo Clinic sites. *When checked, describe in detail the research procedures or activities that will be conducted by Mayo Clinic study staff.*

(1b) Mayo Clinic study staff will be engaged in research activity at a non Mayo Clinic site. *When checked, provide a detailed description of the activity that will be conducted by Mayo Clinic study staff.*

Subject Information

Target accrual is the proposed total number of subjects to be included in this study at Mayo Clinic. A "Subject" may include medical records, images, or specimens generated at Mayo Clinic and/or received from external sources.

Target accrual:

40 healthy adult volunteers (up to 60 healthy subjects, if necessary) will be recruited for this study. More subjects than this will likely have to be approached for potential participation.

Subject population (children, adults, groups):

The subject population will include healthy adult volunteers (over the age of 18).

Inclusion Criteria:

- Adults over the age of 18 and who are willing and able to give informed consent
- Willing and able to participate in all activities related to this study, including trimming chest hair and wearing a reference device and the CPM wearable device
- Volunteers of any race, any gender
- Range of physiques
- Healthy

Exclusion Criteria:

- Injury or skin disturbance in the area of the test device

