[figure not shown]

Title: SAP0002 Clinical Statistical
Analysis Plan

NCT: NCT05445206

	Name	Role / Function	Signature	Date
Prepared By	[name]	Biomedical Systems Engineer		May 11 2022
Reviewed By	[name]	Algorithm Engineer		May 11, 2022
	[name]	Biomedical Engineer, Clinical Trial		May 12, 2022

Introduction:

This document describes the statistical analysis planned for the clinical evaluation data. The study is described in the clinical evaluation protocol (CEPR0002).

Analysis Plan:

Analysis 1: Respiration rate accuracy

The primary objective of this analysis is to demonstrate whether 85% of the errors are bounded within ± 2 bpm. It is noted that we will be using 85% instead of 95% because the CPM system is intended to give a trend, represented by multiple data points over time. This means the errors in the individual data points are averaged out in the trend interpretation, therefore justifying the change from 95% to 85%.

Respiration rate under natural breathing condition, if available, and controlled breathing condition (6, 10, 15, 20, 25, 30, 35, 40 brpm) will be summarized for CPM system and clinician annotated capnography. Although multiple breathing rates conditions are achieved within a subject, each data point is considered independent from each other. Prior look-ahead testing showed that there's no difference in mean errors and median errors across different breathing rate conditions, thereby justifying analyses after pooling all rate conditions together.

The error will be calculated by the difference between the CPM system's estimate and clinician annotated reference for each body posture. The error will be summarized using descriptive statistics and its limits of agreement. If the initial clinician's annotation is strongly suggested to be inaccurate by the compelling evidence (e.g., significant deviation from the simulated breathing or equivalently strong observations), the second annotator may be introduced to read the capnography waveform independently. The final respiration rate is determined based on two annotator readings.

Analysis 1-1: Respiration rate error descriptive statistics

The descriptive statistics includes but not limited to:

- Percentage of the CPM system's RR estimate not reported due to bad signal quality.
- Mean, median, variance, standard deviation, skewness, kurtosis, root mean squared error, and root median squared error.

Analysis 1-2: Percentage of respiration rate error within ± 2 brpm

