Using the data that are classified by the CPM system as good quality, the percentage of the respiration rate whose error is within ± 2 brpm is derived. The confidence interval for the proportion of the errors within ± 2 brpm will also be characterized assuming that the number of data points whose errors are within ± 2 brpm follows binomial distribution.

Analysis 1-3: Respiration rate error limits of agreement

The limits of agreement will be derived using a conventional Bland-Altman analysis as well as non-parametric approach in case the distribution of the error has a long-tail, significant deviation of Normality assumption of the conventional Bland-Altman analysis.

The 85% limits of agreement (bias \pm 1.44 standard deviation) will be tabulated. The 95% confidence interval for the limits of agreement will also be derived. In case the kurtosis, calculated in the Analysis 1-1, is high indicating that the distribution of errors has a long tail, non-parametric limits of agreement will also be presented to correctly characterize the range which 85% of the errors are expected to be bounded by. The non-parametric 85% limits of agreement will also be derived based on 7.5% and 92.5% percentile of the errors. The 95% confidence interval for non-parametric limits of agreement will be derived using a bootstrap resampling method.

Analysis 1-4: Other respiration rate accuracy analyses

A 95% confidence interval (CI) for mean error (i.e., bias) will be tabulated. While the primary objective is to show that the CPM estimate is accurate within ± 2 brpm, the CI for mean error will additionally show if there is any systemic bias in the CPM estimate. The standard deviation of the paired differences will also be tabulated.

If the lower bound of the 95% confidence interval for the percentage of the errors within ± 2 bpm from Analysis 1-2 exceeds 85%, it is demonstrated with statistical significance that the CPM system's respiration rate accuracy is sufficient in comparison to the reference to support its intended use. Also, the other analyses should provide different lenses to characterize the respiration rate accuracy.

Analysis 2: Accuracy of relative changes of relative tidal volume

The primary objective of this analysis is to demonstrate the CPM system's relative tidal volume (rTV) is accurately tracking true changes in tidal volume (TV).

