For each subject, relative tidal volume from the CPM system and the tidal volume from the reference device under the breathing-depth controlled condition (natural ~ 500 mL, shallow ~ 250 mL, deep ~ 750 mL, very deep >1 L) and the breathing-rate controlled condition (e.g., 10, 15, 25, 30 bpm) will be compared for each body posture. A scatter plot of relative tidal volume produced by the CPM system and the tidal volume measured by the reference device will be produced. Each graph will be summarized by two least-squares linear regression fits. One is produced in a linear scale and the other is produced in a log scale to characterize the relative accuracy.

Analysis 2-1: Respiration rate error descriptive statistics

The descriptive statistics includes but not limited to:

- Percentage of the CPM system's rTV estimate not reported due to bad signal quality.
- Mean, median, variance, standard deviation, skewness, kurtosis, root mean squared error, and root median squared error.

Analysis 2-2: Least-squares linear regression analysis in rTV and TV

The accuracy of relative changes of rTV will be summarized by Pearson correlation coefficients across subjects. Then, mean correlations will be determined using Fisher's z-transformation to combine the subject specific coefficients and then back transformed. A 95% confidence interval on mean correlation coefficient will also be derived.

Analysis 2-3: Least-squares linear regression analysis in natural logs of rTV and TV

The accuracy of relative changes of rTV will be summarized by Pearson correlation coefficients across subjects obtained using natural logs of rTV and TV. Then, mean correlations will be determined using Fisher's z-transformation to combine the subject specific coefficients and then back transformed. A 95% confidence interval on mean correlation will also be derived.

After the linear fit, root mean square of the relative residual errors will also be characterized. A 95% confidence interval on the root mean squared relative errors will also be derived using Chi-squared distribution assuming the relative residual errors follows a zero-mean Gaussian distribution.

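### Enrolment depends on the test device being shown to measure on the subject, so people on whom it cannot would be missing from the non-report percentages

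*Protocol*

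**What the plan says.** **Entry.** Protocol, Baseline Evaluation: a subject who satisfies every inclusion criterion and no exclusion criterion "will be considered enrolled once measurement capability of the device on the subject has been verified". The protocol gives no pass criterion for this verification, no number of attempts and no log of failures. It does not say what happens to someone who fails. The Inclusion and Exclusion Criteria do not mention measurability.

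**Population.** The inclusion list asks for "Range of physiques". The Intended Use section says: "The device is intended for use on general care adult patients who are 18 years of age or older".

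**Non-reporting.** SAP Analysis 1-1 lists "Percentage of the CPM system's RR estimate not reported due to bad signal quality" among its descriptive statistics, and Analysis 2-1 does the same for the "rTV estimate not reported due to bad signal quality". Neither states a denominator or an analysis set.

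**Accuracy.** Analysis 1-2 begins "Using the data that are classified by the CPM system as good quality". The success statement at the end of Analysis 1-4 is that if the lower 95% confidence limit "exceeds 85%, it is demonstrated with statistical significance that the CPM system's respiration rate accuracy is sufficient" to support the intended use.

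**Disposition.** The Demographics part of the protocol's Data Analysis Plan tabulates screen failures, enrolled subjects, withdrawals and completers. Failed verification is not named as a category.

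**The concern.** Whether a person enters the study depends on the performance of the device being validated, and the check comes after eligibility has been settled. This differs from the plan's other quality rules. Repeating a poor reading (Study Procedures) acts on single readings, and replacing a broken unit (Malfunctioning or Broken Investigational Devices) acts on hardware. The enrolment condition acts on whole people on whom a working unit cannot measure.

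Two things are at stake. The first is the non-report percentage. The accuracy analysis is restricted to readings that the device itself accepts, so a reader needs the non-report percentage to judge how selective that restriction is. The second is the population to which the conclusion applies. The SAP concludes for the intended use in general adults, while the data would come only from people on whom the device had already been shown to work.

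**Working it through.** **1. The plan's own figures.** The documents give no verification-failure rate, so there is none to reproduce. The nearest planned figure is the respiration-rate sample size, which was checked for any allowance for unmeasurable subjects. Inputs from the Sample Size Justification: SD 3.31 bpm, bias -0.16 bpm, margin ±1 bpm, two-sided α = 0.05, power 90%, 9 readings per subject. With the equivalence formula that splits β between the two sides:

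n = [3.31 × (1.960 + 1.645) / (1 - 0.16)]² = 201.8, rounded up to 202 readings; 202/9 = 22.4, rounded up to 23 subjects.

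Both figures match the protocol. The formula has no term for people who cannot be measured. The increase to 40 subjects is justified by a broader population and possible underestimation of error, not by measurement failure.

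**2. Following a person who fails verification through the planned outputs.**

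- *Items 1-17:* no readings, because the exercises are for those who go on into the study.
- *Analysis 1-1, respiration-rate non-report percentage:* not counted. The person produces no scheduled estimates, and no stated denominator brings them in.
- *Analysis 2-1, tidal-volume non-report percentage:* not counted, for the same reason.
- *Analysis 1-2, proportion within ±2 bpm:* not counted. A person with no usable signal would be absent even without the enrolment condition, because of the good-quality restriction.
- *Analysis 2-3, root mean square relative error:* not counted. An estimate that was never reported cannot enter the fit.
- *Disposition table:* might be counted as a screen failure, but the text does not say so, and the table feeds neither result.

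The enrolment condition therefore makes a definite difference in Analyses 1-1 and 2-1.

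**3. Size.** Assume 40 subjects measured and k further eligible subjects who fail verification. The share of people on whom measurement was attempted but failed, and who are not shown, is k/(40+k):

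- k = 1: 1/41 = 2.4%
- k = 2: 2/42 = 4.8%
- k = 3: 3/43 = 7.0%
- k = 4: 4/44 = 9.1%

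This is a rate per subject. For readings, suppose that the 40 measured subjects have non-report proportion q, and that every scheduled reading of the k others counts as not reported. With equal numbers of readings per subject, the overall proportion is (k + 40q)/(40 + k), which exceeds q by k(1 - q)/(40 + k). The percentages above are therefore the largest understatement for each k, reached when q = 0.

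**The case against.** The strongest reply is that the protocol sentence only defines a label. No passage ties Analyses 1 or 2 to enrolled subjects, and recruitment is counted by subjects who have initiated the study. The exclusion is thus a consequence of the procedure, not a stated rule. That is correct, and it limits how firmly the point can be put. It does not remove the point: someone without scheduled readings is absent from the percentages unless the plan says otherwise, and it does not.

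A second reply is that such people may appear as screen failures, and that signal trouble leads first to remedies (hair trimming, new adhesive, a replacement unit). Both may reduce the number hidden. Neither puts the remainder into a non-report percentage.

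A third reply is that the primary accuracy result is not shown to be affected. This stands. A reader might infer that the ±2 bpm result is itself inflated, and could support that with arithmetic. Take 9 readings per subject, independence as the SAP assumes, and exact 95% limits. An observed 324/360 (90%) has a lower limit of 86.4%. Adding one unmeasured person's 9 readings as misses gives 324/369 (87.8%) with a lower limit of 84.0%. But that quantity is a yield: the share of attempted readings that are both reported and accurate. The 85% criterion is applied to readings graded as good quality, and no document sets a threshold for yield. It also assigns an error where there is neither a device value nor a reference value.

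Finally, the documents do not report that failures occur or why. Body shape, breast tissue or skin contact are possible reasons, not documented ones.

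**Conclusion.** The point holds for non-reporting and for the population to which the conclusion applies. Followed as written, the enrolment condition would leave people on whom a working device cannot measure out of both non-report percentages. For 1 to 4 such people alongside 40 measured subjects, the hidden subject-level rate is 2.4% to 9.1%. This is an illustration: it assumes 40 measured subjects and that those who fail do not proceed, and the true number could be zero.

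The documents do not support the stronger inference that the proportion within ±2 bpm or the tidal-volume error is materially biased. People with no signal would not enter those results in any case. Subjects with marginal signal might, but the direction and size of their effect cannot be established from the documents. The change is worth making before data collection and does not put the primary criterion in question.

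**What to change.** - **Protocol, Baseline Evaluation:** define enrolment as signed consent plus eligibility. Keep verification as a recorded step with a stated criterion, and log every subject on whom it is attempted. Say how this enrolled count relates to the count of subjects who have initiated the study.
- **SAP Analyses 1-1 and 2-1:** state the denominators. Include subjects who fail verification, with their scheduled estimates counted as not reported.
- **Protocol, Data Analysis Plan, Demographics:** add a separate row for failed verification, with the sex, height and weight that the baseline evaluation already collects.
- **Optional:** a version of Analysis 1-2 that counts these readings as not within ±2 bpm, labelled as a yield measure and not as a test of the 85% endpoint.

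The primary criterion and the target of 40 completers do not change. The cost is a reworded enrolment sentence with the verification criterion, a CRF field, the two denominators and a table row, with no new study procedure. The downside for the sponsor is a possibly less favourable non-report percentage. If nobody fails, the sponsor has documented that.
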